4.4 Randomization

For the phase 2 safety study we will first complete the final survey round of the PEOPLE study and then enumerate all those aged 5 years or above, weighing 20 kg or above and not currently suffering from leprosy. They will be divided into three age categories, 5-12 years, 13-17 years, and 18 years and above. We will then determine the overall proportions of the three age groups, the proportion multiplied by 150 will be the number of participants to be recruited per study arm for each age group. Next we will prepare sealed envelopes containing a note indicating either BE-PEP or SDR-PEP as PEP regimen, 300 in total. They will be divided into three groups with equal numbers per PEP regimen, one group of envelopes for each of the three age categories.

The next step will be to enroll the required numbers of adults (age 18 years and above) by visiting the households one by one and inviting eligible subjects to be enrolled. Each time a person agrees, an envelope will be drawn and either SDR-PEP or BE-PEP will be provided as indicated on the note inside the envelope. This process will continue until all envelopes for adults have been allocated. Provided no concerning adverse events are observed, the procedure will be repeated for the 13-17 years old. Again if no concerning adverse events are observed, the 5-12 years old will be enrolled following the same procedure. The remainder of the village population aged 2 years and above and not meeting other exclusion criteria will then be offered SDR-PEP.

Randomization for study arms 1 and 2 of the phase 3 study, will take place upon completion of the baseline survey. We will then arrange all villages by island and by group (former arm 1, 2, 3 or 4 or new villages), in order of decreasing prevalence. As was explained earlier, Fomboni, the capital of Mohéli, will be split into two clusters. Thus we will arrive at 22 pairs of clusters. Blocked randomization will be used to allocate clusters into the two study arms. The randomization schedules will be prepared by an independent sponsor biostatistician. The randomization list will be prepared using SAS 9.4 (SAS Institute, Cary NC).

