11. DATA MANAGEMENT

In the BE-PEOPLE study for the baseline survey we will continue to use formats developed in the PEOPLE study consisting of a paper survey form, three forms in an Android app and an Access database with barcode, name, age and gender of each participant enrolled. After the baseline survey in 2022, which partly overlaps with the final survey of PEOPLE, we will shift from ODK Collect used in the PEOPLE trial to REDCap, which is GCP compliant. REDCap will also be used in the phase 2 study in 2022.

Data Management will be performed by the CTU data managers in collaboration with the Principal Investigator and with the study staff involved in collecting and handling the study data. The continued follow-up of the cohort of leprosy patients established during the PEOPLE trial and the preceding ComLep trial, of which drug resistance surveillance is a part, we also shift to REDCap. Drug resistance surveillance will be extended to tuberculosis patients, data collection for this part will also be integrated in the REDCap database.

A separate Data Management Plan will be prepared, with following essential aspects:

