## 4. Description of study population

### 4.1. Participant accounting

The number of participants screened, those who meet the study inclusion criteria and enrolled (randomized) or excluded will be summarized according to reason for exclusion. Of the enrollees, the number of participants discontinued or lost to follow-up will be recorded by reason and time of discontinuation. Additionally, the number and proportion of participants who were excluded at baseline because of a QTc  $> 450$  ms, as well as the number of exclusions due to elevated AST or ALT will be described by treatment arm and age stratum. These figures will be summarized in a CONSORT flow diagram. A table summarizing the enrolment process by treatment arm will also be produced.

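### Phase 2 allocation by drawing sealed envelopes from a pile has no described safeguard against redrawing, and the SAP would neither undo a redraw nor can it report baseline exclusions by arm

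*Protocol*

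**What the plan says.** Protocol 4.4 gives the whole phase 2 procedure. There are 300 sealed envelopes, each holding a note that names one regimen. On how they are sorted, the protocol says: "They will be divided into three groups with equal numbers per PEP regimen". Each of the three age strata has its own pile. Staff then visit households and invite people described as eligible. The draw itself is described as follows: "Each time a person agrees, an envelope will be drawn and either SDR-PEP or BE-PEP will be provided as indicated on the note". Drawing goes on until the adult pile is used up, and the younger strata follow in the same way. Sealing is the only safeguard named. The independent sponsor biostatistician appears only in the phase 3 paragraph of 4.4.

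Other relevant places:

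- **Baseline QTc.** Protocol 5.1 and 7.2.1 put an ECG within the week before dosing and use the result for eligibility.
- **Blinding.** Protocol 5.1 says the differing regimens make blinding impossible. Protocol 7.2.1 does provide blinded review of the stored ECGs.
- **Order of events.** Table 2 in Protocol 5.1 puts consent, criteria, ECG and ALT/AST at Screening and randomization at D0. SAP 2.1 also randomizes eligible individuals.
- **Analysis sets.** SAP 5.1 and 5.1.1 analyse both the per-protocol and ITT sets by treatment administered. Protocol 9.1 defines ITT by randomized allocation. Both documents make per-protocol the primary phase 2 set.
- **Primary rule.** SAP 6.1 compares the one-sided 95% upper limit for the day-1 difference in mean QTc with +10 ms. ANCOVA on baseline QTc is also planned, with change scores as an alternative.
- **Exclusions.** SAP 4.1 covers baseline exclusions for QTc, "as well as the number of exclusions due to elevated AST or ALT will be described by treatment arm and age stratum".

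**The concern.** Drawing from a pile differs from opening the next envelope in a fixed sequence. If nothing ties an envelope to a participant before it is opened, an unwelcome note can be returned and another taken without trace. The incentive is easy to see: a field worker who knows that someone has a high QTc or looks unwell may prefer that this person not receive bedaquiline. Such steering lowers mean QTc, and perhaps the number of symptom reports, in the BE-PEP arm. Both effects make BE-PEP look safer, and the results go to the DSMB that advises on phase 3.

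The later steps do not repair this. An analysis by treatment administered accepts whichever note was finally acted on. The stated non-inferiority criterion is not adjusted for baseline.

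The SAP 4.1 table is a separate, smaller problem: it asks for an arm for people who were never randomized.

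**Working it through.** **1. The plan's own figure.** Protocol 4.3 gives SD 20 ms, margin +10 ms, one-sided 95% limit, 150 per arm, true difference 0 and power 99%. The standard error is 20 × √(2/150) = 2.31 ms, and 10/2.31 = 4.33. Power is Φ(4.33 − 1.645) = Φ(2.685) = 99.6%, so the stated 99% reproduces.

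**2. Size of a redraw effect (illustration).** Take QTc as normal with mean 384 and SD 20 ms (Protocol 4.3). Suppose staff act on values above 420 ms; that threshold is an assumption. Then z = (420 − 384)/20 = 1.8, the upper tail is p = 0.0359, and the mean excess over 384 in that tail is 20 × φ(1.8)/0.0359 = 43.9 ms. If a fraction f of these people who drew BE-PEP end in SDR-PEP, and m = f × p:

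- BE-PEP shift = −m × 43.9/(1 − m)
- SDR-PEP shift = +m × 43.9/(1 + m)

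| Case | f | BE-PEP shift | SDR-PEP shift | Difference |
|---|---|---|---|---|
| Redrawn until SDR-PEP appears | 1 | −1.64 | +1.52 | −3.2 ms |
| One redraw, about half return BE-PEP | 0.5 | −0.80 | +0.78 | −1.6 ms |

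A simulation with finite piles (75, 35 and 40 per arm; the split of minors is assumed) and a single redraw for the top 10% of baseline QTc gave −1.9 ms if done half the time and −3.3 ms if always done. Always redrawing for the top 20% gave −5.5 ms, an extreme case.

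**3. Carry-over to 24 hours.** The documents give no baseline-to-24-hour correlation r. Assume 0.5 to 0.9 with equal SDs; the unadjusted shift is then r times the baseline shift.

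- From 1.6 ms: 1.6 × 0.5 = 0.8 to 1.6 × 0.9 = 1.4 ms
- From 3.2 ms: 3.2 × 0.5 = 1.6 to 3.2 × 0.9 = 2.9 ms

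This is at most about 1.2 standard errors (2.9/2.31). If the true difference is 0, non-inferiority would be declared in about 99% of trials anyway. The shift matters only if the true difference lies near the margin.

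**4. Predictability of the pile.** For m envelopes per regimen, always guessing the regimen with more left gives m + (4^m/C(2m,m) − 1)/2 correct guesses out of 2m. The expected number of final draws known with certainty is 2m/(m + 1).

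| m per regimen | Correct guesses | Certain final draws |
|---|---|---|
| 75 | 54.8% | 1.97 |
| 25 | 57.9% | 1.92 |
| 20 | 58.7% | 1.90 |

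With 75, 35 and 40, the total is 55.7%: about 17 extra correct guesses in 300 (0.057 × 300), and about 6 certain draws. The same formula gives 70.8%, 68.3% and 66.6% for blocks of 4, 6 and 8. Small blocks would therefore make guessing easier.

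**5. Order of events.** Protocol 4.4, Table 2 and SAP 2.1 agree that eligibility comes first. SAP 4.1 is the only outlier, and its by-arm cells cannot be filled for people excluded at baseline.

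**The case against.** - **Silence is not proof.** The envelopes are sealed, and no text says that they are unnumbered. No text says who draws, or whether that person has seen the QTc. This stands: the finding is that safeguards are not described, not that they are absent in practice. A written procedure that says only that an envelope is drawn still permits a redraw.
- **Baseline adjustment is planned.** ANCOVA targets steering on QTc, and disagreement with the unadjusted result would be a warning. Baseline characteristics are also shown by arm (SAP 4.2), and ECGs have blinded review. This removes much of the QTc concern. It does not cover steering on general health or the open-label symptom reports, and the stated criterion remains unadjusted.
- **The shift is an extreme case.** The 3.2 ms needs every eligible redraw to happen and succeed. This stands, and is why the range starts at 1.6 ms and falls further at 24 hours.
- **Early knowledge of allocation.** A reader might infer from SAP 4.1 that envelopes are opened before eligibility is settled. The documents do not support that: three places put eligibility first, and SAP 4.1 reads as a drafting slip.
- **The gate to phase 3.** A reader might infer that a biased non-inferiority test would by itself open phase 3. Protocol 2.1.1 and 8 make the outcome DSMB advice, based on QTc data, adverse events and stopping criteria, with the relevance of any QTc prolongation left to the board's judgement.

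**Conclusion.** The concern holds as a gap in the specification of allocation concealment. As written, Protocol 4.4 neither prevents a redraw nor leaves a trace of one, and the SAP's as-administered ITT, which conflicts with Protocol 9.1, would not correct it. The direction would favour BE-PEP. The size is modest: about 1.6 to 3.2 ms at baseline and about 0.8 to 2.9 ms at 24 hours, against +10 ms. This rests on the plan's mean and SD, an assumed 420 ms threshold and an assumed correlation of 0.5 to 0.9. The planned ANCOVA or change-score analysis covers part of it. Predictability from exhausting the pile is real but minor.

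The documents do not show that redrawing occurred or that the envelopes lack numbers. The by-arm exclusion table in SAP 4.1 is a separate, definite error, given the order of events stated elsewhere.

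**What to change.** **Protocol 4.4.**

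- Have the independent biostatistician prepare the phase 2 list, keeping one large permuted list per age stratum. Do not introduce small or varied small blocks.
- Use sequentially numbered opaque envelopes opened strictly in order, or central release. "REDCap will also be used in the phase 2 study in 2022" (Protocol 11), but the protocol describes REDCap for data capture, not allocation, so that route would need setting up.
- Write the participant number on the envelope before opening it. Open it only at D0, after the result of every eligibility criterion is recorded.
- Reconcile all 300 envelopes against a log.

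**SAP.**

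- In 4.1, report baseline QTc and ALT/AST exclusions overall and by age stratum, not by arm.
- In 5.1 and 5.1.1, define ITT by randomized allocation, as in Protocol 9.1. This is useful only with the log, since otherwise the first envelope opened is not on record.

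If enrolment is complete, the SAP changes can still be made, and the report should state how the envelopes were controlled.

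The cost is some rewording and slightly more paperwork in the field. The 150 per arm and the 99% power do not change.

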4.5 Withdrawal and termination of the study

4.5.1 Reasons for Withdrawal from the study

Participants may be withdrawn from the study if they withdraw consent.

4.5.2 Reasons for Withdrawal from the study intervention

Participants may be withdrawn from the study intervention if, in the opinion of the investigator, it is medically necessary, or if it is the wish of the subject. Examples of this are

- When a patient is found to be pregnant
- Treatment limiting adverse events (e.g. kidney or liver failure, or severe vomiting)
- Need for medication that interferes with study medication
- Changes that make patients no longer eligible for the study intervention according to inclusion criteria

Patients that are withdrawn from the study intervention will still be followed up as planned, since they will be analyzed in the ITT population.

4.5.3 Handling of Withdrawals

For participants that withdraw consent, no further evaluations will be performed, and no efforts to collect information will be carried out. These participants will be referred to routine care for further treatment if required.

For participants withdrawn from the study intervention, thorough efforts will be made to document study outcomes and safety data (three attempts to contact the participant in his/her home unless it is clear that the participant will not return or refuses further contacts). Participants will be scheduled for their regular follow-up visits, will undergo all study procedures and will be analyzed in the ITT analysis until the end of the study. Data collected up to the time of withdrawal will remain in the study data base and be used for analysis whether or not the participant continues with the follow-up visits.

Participants withdrawn from the study intervention for medical reasons will be referred to adequate health facilities for further care if necessary. The reason for withdrawal will be documented on the CRF.

4.5.4 Lost to follow-up

Patients will be considered lost to follow-up if not present during the fourth and final survey round, after one additional attempt has been made to contact them. In this case follow-up time will be calculated based on the last available follow-up.

4.5.5 Termination of Study

The end of the study is defined as the date of the last visit (or last contact) of the last patient in the study.

If the study is prematurely terminated or suspended, the Sponsor will promptly inform the investigators/institutions, and the regulatory authority(ies) of the termination or suspension and the reason(s) for the termination or suspension. The ECs will also be informed promptly and provided the reason(s) for the termination or suspension by the Sponsor or by the investigator/institution, as specified by the applicable regulatory requirement(s).

5. STUDY PROCEDURES

5.1 General Study Procedures

The study has been planned in two phases. The main, phase 3 study will be preceded by a phase 2 study in the village of Gégé on Anjouan. In this village we will conduct door-to-door screening for leprosy in May, 2022, coinciding with the final screening round of the PEOPLE study. We will then ask for informed consent for inclusion in the phase 2 study of BE-PEOPLE. To those who consent we will provide post exposure prophylaxis with BE-PEP or SDR-PEP with intensified safety monitoring, as was described in chapter 4.4 above. Safety monitoring will include an ECG taken less than 1 week before treatment and approximately 24 hours after treatment, as well as liver function tests less than 1 week before and 14 days after treatment. In case of an ALT/AST elevation adverse event on visit D14 or absolute AST/ALT value increase of ≥ 35 between the prerecruitment visit and visit D14, liver function tests will also be included on visit D30. The team, including a medical doctor will be present during the PEP administration round (=D0), as well as the day after (=D1) to collect safety data (including QTc). The team, again including a medical doctor, will investigate the participant at the study center 14 days after (=D14) to collect additional safety data (ALT + AST) and to follow up on any ongoing (S)AE's. In case any SAE's are ongoing during the visit on D14 additional visits will be organized to follow up. A final visit to collect adverse events will be organized on D30 at the participant's house. In case liver function tests are necessary on visit D30, the participant will be invited to the study house for visit D30.

In case of any serious adverse events, transport to the hospital in the island capital Mutsamudu will be ensured, where cardiological care is provided including monitoring, electrolyte correction, and cardiac resuscitation. A project vehicle will be on standby in the village for this purpose. The results of this phase 2 safety study will be presented to the data safety monitoring board (DSMB), involved ethical committees, and local regulatory authority who will provide an opinion on whether or not the green light can be given for the main phase 3 study.

Ahead of the main phase 3 study and partially overlapping with the phase 2 study we will conduct the baseline screening which will cover 34 villages already part of the PEOPLE study (part of PEOPLE study), plus nine additional villages (specific for BE-PEOPLE study). Conditional on a positive advice by the DSMB and approval by the applicable (local) ethical and regulatory authorities, randomization will take place after screening activities in all villages are finished for the phase 3 study to start.

During the phase 3 study, each village will be screened door-to-door annually for four in a row years starting in 2023. Every year the PEP zone will be determined in each village and PEP will be provided to those eligible. Prior to the start of the study the village elders will be informed on procedures and purpose of the study, followed by community sensitization. During the first screening for leprosy, residents of the selected villages will be checked for eligibility informed on all study procedures, and requested to provide informed consent. Those previously enrolled in the PEOPLE trial will be asked informed consent for enrolment in the new trial in 2023, once we know to which study arm they have been randomized. Participants in the new villages will be asked informed consent twice, first for the baseline screening and again in 2023, when we know to which study arm they have been randomized.

After informed consent has been obtained, the health worker will perform a physical examination to look for signs of leprosy and TB. Diagnosis of leprosy will be made based on the so-called cardinal signs, i.e. a patch with loss of sensation, enlarged peripheral nerves and/or a slit skin smear positive for acid fast bacilli. Results of qPCR testing will not be used as diagnostic criteria, as the test is at best 85% sensitive, less so in paucibacillary patients. For patients with doubtful clinical signs, the diagnostic team does not classify them as having leprosy, yet revisits them in subsequent months for repeat

diagnostic investigation, per routine care. The health worker will also collect the necessary additional personal information from every individual enrolled.

Afterwards the PEP zone will be determined and a list of households living in the PEP zone will be provided to the teams who will revisit the participants. In case the participant is eligible for PEP (i.e. belonging to a household in the PEP zone and individual PEP inclusion/exclusion criteria are respected), the correct dose of bedaquiline and/or rifampicin will be distributed according to the schedule below:

- <10 kg or age <2 years : No PEP
- ≥10-<20 kg and age 2-4 years : rifampicin:150 mg
- ≥20-<30 kg and age ≥5 years : bedaquiline*: 400 mg, rifampicin: 300 mg
- ≥30-<45 kg : bedaquiline*: 800 mg, rifampicin: 450 mg
- =>45 kg : bedaquiline*: 800 mg, rifampicin: 600 mg

*Arm 1 only to participants eligible for BE-PEP

The health worker will offer a snack and a drink to assist with the ingestion of the pills and will witness the intake of the medication by the participant and enter relevant information in a designated app. All participants enrolled on PEP, will be re-visited by a health worker the next day (safety FU visit, window defined in table 3) to ask whether the PEP has not been vomited up and whether there have been any (serious) adverse events ([S]AE). In case of ongoing SAE's at the safety FU visit, the team will conduct follow-up. In case PEP has been vomited, this will be recorded but the dose will not be repeated.

The nature of the trial, requiring intake of different PEP regimens in different arms, makes blinding impossible. We will however use additional approaches to validate study results and detect possible observer bias, such as quantitative PCR (qPCR) testing of skin biopsy samples from leprosy patients diagnosed in both study arms.

If a screened person is diagnosed with leprosy or TB, he/she will be requested to sign an additional consent form for the collection of samples. Irrespective of further participation in the study, this person will be treated as per the standards of the National Leprosy Control Program.

Tables 2 and 3 below provide an overview of assessments during phase 2 and 3 respectively.

TABLE 2: SCHEDULE OF ASSESSMENTS PHASE 2

	Screening	Enrollment	Day 1 (V1)	Day 14 (V2)	Day 30 (V3)
Timing (window)		D0	D1 (+0 d.)	D14 (+-2 d.)	D30 (+3 d.)
Medical history¹	X				
Inclusion/exclusion criteria	X				
Randomization		X			
Informed Consent	X				
Clinical examination	X	X			
Blood sample for ALT/AST	X			X	(X) ⁴
ECG	X		X		
IP Administration³		X			
Concomitant medication⁴	X	X	X	X	
Adverse Event collection		X	X	X	X

1 Medical history deemed medically relevant for the study will be collected before signing informed consent to participate in the phase 2 trial.

2 All PEP treatment will be delivered by the health worker and intake will be directly observed.

3 Concomitant medication should be recorded from 3 weeks before D0 (day of IP administration) until 3 weeks after IP administration. After that concomitant medication should only be reported if given for an SAE.

4 In case of an ALT/AST elevation adverse events on visit day 14 or absolute AST/ALT value increase of ≥ 35 between the prerecruitment visit and visit day 14, liver function tests will also be included on visit day 30. In this case the participant will be invited to the study house to conduct visit D30.

TABLE 3: SCHEDULE OF ASSESSMENTS PHASE 3

	Screening Y1 – Y4	PEP zone Y1 – Y3	PEP 1st dose Y1 – Y3	Safety FU Day 1 Y1 – Y3	PEP 2nd dose BE-PEP⁶ Y1 – Y3	Safety FU 2nd dose Day 1 Y1 – Y3
Timing (window)	- V1 - V2: V1+365 (+-90) - V3: V2+365 (+-90) - V4: V3+365 (+-90)	- V1+25 (+-25) ⁹ - V2+25 (+-25) ⁹ - V3+25 (+-25) ⁹	- D0:V1+30 (+-30) ¹⁰ - D1:V2+30 (+-30) ¹⁰ - D2:V3+30 (+-30) ¹⁰	- D0 +1 (+3) - D1 +1 (+3) - D2 +1 (+3)	- D0*: D0 + 30 (+-7) - D1*: D1 + 30 (+-7) - D2*: D1 + 30 (+-7)	- D0* +1 (+3) - D1* +1 (+3) - D2* +1 (+3)
Enrolment participant¹	X		X ⁷			
Informed Consent	X ²		X ⁷			
Leprosy & TB physical examination	X		X ⁷			
Eligibility based on PEP zone³		X				
PEP Eligibility based on PEP Inclusion/exclusion criteria			X		X	
IP Administration^{4,5}			X		X	
Adverse Event collection			X	X	X	X
Leprosy and/or TB sampling⁸	(X)		(X)			

- 1 Every year new household members/household can be added to the study population
- 2 For new BE-PEOPLE villages (not included in the PEOPLE study) a baseline screening ICF is collected during the first screening visit. For villages enrolled in the PEOPLE study, informed consent was collected in this study to collect data and to share data with future research such as the BE-PEOPLE study.
- 3 PEP zone: Anyone living within a 100 meter radius of an index case or to the entire village if more than 50% of the population lives within a 100 meter radius of an index case
- 4 Conditional on Leprosy & TB physical examination, PEP inclusion and exclusion criteria and exposure to index cases
- 5 All PEP treatment will be delivered by the health worker and intake will be directly observed.
- 6 In arm 1, household contacts of an index case will receive an extra dose of BE-PEP after 4 weeks
- 7 Household members living in a household eligible based on the PEP zone but absent during screening can be enrolled and screened during the 1st dose PEP administration visit and receive PEP if eligible
- 8 If leprosy or TB clinical signs present, after collecting a specific ICF for leprosy index case or TB suspicion, samples to be collected.
- 9 +-25 after the last person screening (=V1) in a village during the annual screening round
- 10 +-30 days after the last person screening (=V1) in a village during the annual screening round

For all visits, especially important for safety FU visits: if a participant is not home (and is not permanently absent), the site staff should visit the household at least one more time to conduct the visit. Participants will be informed they may always report adverse events by phone

